13. DATA MANAGEMENT

Each site will be responsible for accurate, complete, and timely collection/recording of data using the CRF (or EDC system) provided. Data will be stored in a validated and secure database for analysis. ConforMIS will periodically review all data, and specifically adverse event data to determine interim revision rates, frequency of serious adverse events and patient outcomes. If

missing data fields or incorrect data are identified, the site may be contacted to provide the missing/correct data.

ConforMIS or a designee will provide Case Report Forms (paper and/or electronic) to the study sites, along with access to the EDC system.

14. MONITORING

ConforMIS or designee will monitor clinical sites using risk-based monitoring to review source data, study conduct, and compliance to the protocol. Each site will be monitored shortly after beginning enrollment to ensure early identification and resolution of any issues. After the initial monitoring visit, the site will be monitored at a frequency determined by ConforMIS or designee based on a variety of variables including but not limited to the risk of the site, rate of enrollment, the number of issues identified that require follow-up, changes in site personnel, etc.

15. STATISTICAL METHODS

All statistical processing will be performed using SAS® Version 9.3 or later unless otherwise stated.

For continuous variables, descriptive statistics will include n (number of subjects), mean, standard deviation (SD), median, minimum, and maximum. For categorical variables, the number and percentage of subjects in each category will be presented. Appropriate inferential statistics will be used for the primary and secondary efficacy variables.

Populations

The safety population will be comprised of all subjects for whom the procedure is initiated.

The Full Analysis Set (FAS) will be comprised of all subjects for whom the procedure is completed.

The Per-Protocol (PP) population will include all subjects in the FAS who complete the 1 Year visit without significant protocol violations. The PP population will not include subjects who meet any of the following criteria:

- Violated inclusion/exclusion criteria, without sponsor waiver;
- Did not attend the 1 Year visit
- Out of window at the 1 Year visit by +/- 2 months
- Have undergone a procedure to the contralateral knee which may impact the follow-up assessments

Additional criteria may be added to the list to accommodate for unforeseen events that occur during the conduct of the study that impact efficacy assessments. The PP population will be determined prior to data base lock.

Demographic and Baseline Characteristics

Demographic variables (e.g. age, gender, ethnicity, race) and baseline characteristics will be recorded in the CRF. For continuous variables, comparisons between treatment groups will be

conducted with an analysis of variance (ANOVA). A Cochran-Mantel-Haenszel (CMH) test will be used for testing categorical variables.

Efficacy Analysis

Primary Efficacy Analysis

The absolute change from baseline to 1 Year for each primary endpoint will be analyzed using an analysis of covariance (ANCOVA) with factor of treatment (iTTotal CR, OTS) and the respective baseline score as a covariate. The least squares means will be presented along with the observed means.

Secondary Efficacy Analyses

Secondary endpoints will be analyzed as follows:

- The absolute change from baseline to 1 Year for each subscale of KSS will be analyzed using an analysis of covariance (ANCOVA) with factor of treatment (iTTotal CR, OTS) and the respective baseline score as a covariate. The least squares means will be presented along with the observed means.
- The absolute change from baseline to 1 Year for each subscale of KOOS will be analyzed using an analysis of covariance (ANCOVA) with factor of treatment (iTTotal CR, OTS) and the respective baseline score as a covariate. The least squares means will be presented along with the observed means.
- Post-operative limb alignment will be dichotomized as in and out of “safe zone” (+/- 3 degrees neutral mechanical axis alignment). The proportion of subjects in each study arm summarized and compared using a CMH test.

Safety Analysis

Procedure-related and device-related adverse events (AEs) occurring during the study will be recorded. For the safety population, AEs will be summarized by study arm, the number of subjects reporting AEs, severity, relationship to procedure, relationship to device, and seriousness.

In addition to overall AE summaries, AEs will be summarized for the following study periods:

- Day of procedure to 6 months post procedure
- Annual summaries (1 Year, 2 Year, etc.) from day of procedure

All serious adverse events (SAEs) will be summarized by study arm, severity, relationship to procedure, and relationship to device. SAEs will also be listed by subject.

All information pertaining to AEs noted during the study will be listed by subject.

The Fisher’s Exact test will be used to compare the proportion of subjects in each study arm who have the following:

- procedure-related AEs
- device-related AEs
- revision procedures

Missing Efficacy Data Imputation

The last observation carried forward (LOCF) method will be used to impute missing efficacy data.

Sample Size Determination

A total sample size of a minimum of 450 and a maximum of 600 subjects will be prospectively enrolled in a consecutive fashion, to each arm of the study (approximately 225-300 in the iTotal CR arm and 225-300 in the OTS arm). To ensure that enrollment in each arm remains relatively even, sites assigned odd site numbers will begin by enrolling off-the-shelf subjects and even numbered sites will begin by enrolling ConforMIS subjects. Based on data from a previous study, it is expected that a minimum of 450 and a maximum of 600 total subjects will provide greater than 80% power for the primary functional endpoint.

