3. STUDY DESIGN

This is a prospective, blinded, multi-center study that will be conducted in the US, UK, and Germany. The study will include a minimum of 450 and a maximum of 600 subjects across up to 20 sites with up to 225 min- 300 max subjects in the iTotal CR arm and 225 min- 300 max subjects in the off-the-shelf total knee arm. An additional 25% may be enrolled to account for subject discontinuation.

Subjects will be consecutively recruited in groups of 10, alternating between study arms until enrollment is completed. Once a series of 10 is recruited (subject signed consent and completed pre-op questionnaires), then the next series of 10 is to be recruited.

To ensure that enrollment in each arm remains relatively even, sites assigned odd site numbers will begin by enrolling off-the-shelf subjects and even numbered sites will begin by enrolling ConforMIS subjects. Subjects will be implanted with either an iTotal CR or an off-the-shelf cruciate retaining total knee replacement.

The person administering the functional tests will be blinded. The blind will be maintained for at least one year in order to maintain an objective assessment of each patient's function. Investigators and study staff will make every attempt to maintain the blind by limiting access to study data, x-rays, and other evaluations.

For all surgeries, the preferred surgical approach is to make an incision that is midline or slightly medial to midline, followed by a parapatellar arthrotomy, or a subvastus arthrotomy with prior written approval from Sponsor. The surgeon must use the same approach for all study subjects.

For surgical technique, the off-the-shelf goal is to obtain mechanical alignment.

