10. ENROLLMENT

Potential subjects will be identified by the Investigator or study staff based on patients' clinical and radiographic assessments during regular medical care. The Investigator or study staff will provide study information and the approved Informed Consent Form to all eligible subjects, (determined via Inclusion/Exclusion criteria), as well as answer any questions about the study.

Once the consent form is signed, the subjects will be assigned a unique subject identification number through the EDC system. Once they complete the first set of pre-operative questionnaires, they will be assigned to one of two treatment arms: A) Treatment with the iTotal CR or B) Treatment with an off-the-shelf knee replacement. The site will be instructed to consecutively enroll 10 subjects per treatment arm, alternating between each arm, until enrollment is completed.

The subject identification number will be comprised of a five digit number starting with a two digit site number assigned by ConforMIS at the Site Initiation followed by a three digit subject number, assigned chronologically for the entire study. For example, at site 01, the first subject enrolled will receive number 01-001, followed by 01-002, 01-003, etc.

The Investigator and/or study staff will assess the subject against the Inclusion and Exclusion criteria to determine eligibility. Eligibility includes clinical assessments, radiographic assessments, and a review of the subject's medical history. The radiographic assessments should include:

1. Knee x-ray: 3 views – AP, lateral, sunrise or Merchant
2. Three foot standing x-ray (full length, full weight-bearing film): AP view

If the subject is not eligible to participate in the study, the subject will not be enrolled and is considered a screen failure. All screen failures will be tracked by the site manually in a tracking spreadsheet and electronically in a clinical database. Subject identification numbers for screen failures will not be re-used.

The following Case Report Forms will be completed for all screen failures:

- SUBJECT INFORMATION/MEDICAL HISTORY
- INCUSION/EXCLUSION CRITERIA

If the subject is eligible to participate in the study, they will be assigned to a treatment arm and will be considered enrolled when they are implanted with a device.

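### The ALF, KSS and KOOS ANCOVAs adjust only for the baseline score although allocation is a foreseeable, non-randomised alternation of tens; a fixed list of collected baseline covariates, plus site, should be pre-specified.

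*Combined protocol and SAP*

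**What the plan says.** **Models.** For the primary analysis, Section 15 says: "The absolute change from baseline to 1 Year for each primary endpoint will be analyzed using an analysis of covariance (ANCOVA) with factor of treatment". The only other term is the respective baseline score. Each KSS and KOOS subscale gets the same two-term model.

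**Allocation.** Section 3: "Subjects will be consecutively recruited in groups of 10, alternating between study arms until enrollment is completed". Section 10: "The site will be instructed to consecutively enroll 10 subjects per treatment arm, alternating between each arm, until enrollment is completed". Odd-numbered sites start with off-the-shelf implants and even-numbered sites with the sponsor's implant.

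**Blinding.** Section 3: "The person administering the functional tests will be blinded". No blinding of recruiters or surgeons to the series being filled is described.

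**Baseline data.** Section 15: "Demographic variables (e.g. age, gender, ethnicity, race) and baseline characteristics will be recorded in the CRF". Arms are compared by ANOVA for continuous variables; otherwise, "A Cochran-Mantel-Haenszel (CMH) test will be used for testing categorical variables". None of these variables enters an efficacy model.

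**Small sites.** Section 9 has an oversight committee that includes a statistician, and allows data from a site with fewer than 20 subjects to be left out of the analysis.

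**The concern.** Under randomisation, baseline differences between arms are chance differences, and the standard error allows for them. Alternation from a known starting arm gives no such assurance, because whoever approaches and consents a patient can know which implant the current series receives. A difference between arms in age, sex or another prognostic variable then becomes bias in the treatment estimate, except for the part carried by the baseline score.

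The plan collects the variables and tests them between arms, but gives no adjusted model. If an imbalance appears, any adjustment will be post hoc and chosen with the tests in view. At stake is whether a difference in one-year function can be credited to the implant.

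**Working it through.** **1. The plan's own figure.** The sample-size paragraph of Section 15 claims more than 80% power with 450-600 subjects. It gives no effect size, SD or alpha, so the claim cannot be reproduced. With an assumed two-sided 5% test, the standardised difference detectable with 80% power is (1.96 + 0.84) x sqrt(2/n):
- n = 225 per arm: SE 0.0943, difference 0.264 SD
- n = 300 per arm: SE 0.0816, difference 0.229 SD

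**2. Confounding (illustration; both inputs assumed).** Bias = imbalance x partial correlation with the outcome.
- Low: 0.1 x 0.2 = 0.02 SD. High: 0.2 x 0.3 = 0.06 SD.
- Share of the detectable effect: 0.02/0.264 = 8%; 0.06/0.229 = 26%.
- Shift of the test statistic: 0.02/0.0943 = 0.21, type I error 5.5%; 0.06/0.0816 = 0.73, type I error 11.4%.

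**3. Which term removes it.** Alternating tens were simulated in 15 assumed sites (about 450 subjects, 2,000 runs per scenario, site ICC 0-0.2), with a covariate of assumed coefficient 0.3 shifted by an assumed 0.3 SD between arms. This is a larger shift than in step 2. Type I error was:
- treatment + baseline: 13%-17%
- plus site: 15%-19%
- plus site and the covariate: 4%-5%

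With no shift, all three models stayed near 5%. The patient-level covariate does the work; site does not.

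**4. What omitting site does to the standard error.** Let t be the residual site ICC after baseline adjustment (assumed; none is given), with no correlation within a series. Then (true SE / model SE)^2 = 1 - t + t x [sum over sites of (nT_j/nT - nC_j/nC)^2] / (1/nT + 1/nC).
- 15 sites x 4 series (N = 600): arms balance within site, so the ratio is sqrt(1 - t). At t = 0.1 it is 0.949, type I error 3.9%.
- 20 sites x 3 series (N = 600): the sum is 20 x (20/300 - 10/300)^2 = 0.0222; divided by 2/300 it is 3.33. The ratio is sqrt(1 + 2.33t). At t = 0.1 it is 1.111, type I error 7.8%. This is the worst case.
- 20 sites, each stopping at random between 20 and 40 subjects: average 5.1% (5th-95th percentile 4.6%-5.5% at t = 0.1).

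**5. Power with and without site, at the differences in step 1.** Site-model SE = sqrt((1 - t) / sum of nT_j x nC_j / n_j).

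| Layout | t | SE with site | Power with site | Power without |
|---|---|---|---|---|
| 15 x 4, N = 600 | 0.1 | sqrt(0.9/150) = 0.077 | 84% | 81% |
| 20 x 3, N = 600 | 0.1 | sqrt(0.9/133.3) = 0.082 | 80% | 78% |
| 15 x 3, N = 450 | 0.1 | sqrt(0.9/100) = 0.095 | 80% | 78% |
| 20 x 3, N = 600 | 0 | sqrt(1/133.3) = 0.087 | 75% | 80% |

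Power without site is the normal probability below 0.84 / SE ratio: 0.84/0.949 gives 81%, and 0.84/1.111 gives 78%.

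**6. Correlation within a series.** A site term does not correct it. In simulation (15 x 4, site ICC 0.1, series ICC 0.02, both assumed; 5,000 runs), type I error was 7.7% with site and 6.3% without.

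**The case against.** The strongest reply is that the design already has safeguards and no imbalance has been shown. The baseline score is in the model, alternation runs within site, starting arms are opposed, eligibility is common to both arms, and all patients considered are logged (Section 8). The timed tests have a blinded administrator, and an oversight committee reviews data integrity. All of this is true. Apart from the baseline score, however, none of it adjusts the estimate.

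Several further points stand:
- **Selection.** A reader might infer that patients are or will be steered between arms. The documents do not support this. Subjects must be told that the device is commercially available (Section 17), but the arm is assigned after consent and questionnaires (Section 10), and nowhere are patients said to be told the coming series. Foreseeability makes selection possible, not demonstrated.
- **Site.** A reader might infer that a site term guards against selection, or that leaving it out inflates type I error. Step 3 contradicts the first. Step 4 shows the second only when many sites stop unevenly; under random stopping the rate is about right on average.
- **Sources of site variation.** Staircase length (minimum 4 steps against a usual 12; the same staircase requested only where possible) bears on the timed tests, not on KSS or KOOS, and baseline ALF absorbs part of it. The choice of control implant varies only in the off-the-shelf arm, and an additive site term cannot remove that.
- **Assigned but not implanted.** Subjects "will be considered enrolled when they are implanted with a device", and "The Full Analysis Set (FAS) will be comprised of all subjects for whom the procedure is completed". Losses between assignment and surgery are a separate population question that no model term addresses.

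**Conclusion.** The point holds as a gap in pre-specification. All three efficacy models omit every measured baseline variable except the baseline score, under a non-randomised and foreseeable allocation. Measured differences between arms are therefore left in the estimate.

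The size is unknown. The 0.02-0.06 SD bias rests on an assumed imbalance, an assumed correlation and an assumed two-sided 5% alpha; it shows scale and is not a forecast. The case for site is modest: 2-3 points of power at an assumed site ICC of 0.1, and a loss if that ICC is zero and stopping is uneven.

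A reader might also infer that an adjusted model would make the comparison as good as randomised. It would not. Patient or surgeon preference may act through factors that age, sex and scores do not capture. This should be fixed, with moderate confidence; it does not show that the planned result would be wrong.

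**What to change.** In Section 15, before any outcome data are seen:
- Specify the main ANCOVA as treatment, respective baseline score, age, sex, and baseline KOOS (in the ALF and KSS models) or baseline ALF (in the KOOS models). Name the KOOS score or subscale.
- Add BMI only if the CRF holds it as a value. Decide that now, not from the baseline tests.
- Include site as a fixed effect because allocation runs within site, giving precision and uneven stopping as the reasons. Pool one-arm or very small sites by a stated rule that agrees with the Section 9 provision for sites under 20 subjects.
- Keep treatment + baseline as a sensitivity analysis. A model with a random effect for series within site is an optional further check.
- State that adjustment cannot remove unmeasured confounding from foreseeable allocation, and word causal conclusions accordingly.

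**Cost.** SAP wording and a few lines in the SAS already named. Site, age, sex, KOOS and the timed tests need no new data. With 20 sites, site uses about 19 degrees of freedom. At site ICC 0.1 and no series variance, power is about 80%-84% with site against 78%-81% without; at site ICC zero with all sites stopping at three series, it falls from 80% to 75%. Correlation within a series stays uncorrected in the main model.

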6. STUDY DURATION

The study subjects will be required to complete follow-up visits at predetermined intervals for 10 years post-implantation. The in-office follow-up visits will occur at 90 days, 180 days, 1 year, 2 years, 5 years, and 10 years post-implantation. The remaining follow-up data collected at years 3, 4, 6, 7, 8, and 9 may be collected via phone call, mail, or email and does not require an in-office visit.

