7.2. Secondary Endpoints

The study secondary endpoints are:

1. The 2011 Knee Society Knee Scoring System[®] (KSS) and/or its subscales at 1 Year post-implantation
2. The Knee Injury and Osteoarthritis Outcome Score (KOOS)
3. Incidence of major procedure-related and device-related complications, including revision rates
4. Post-operative limb alignment

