On the anniversary of the implant surgery for years 3, 4, 6, 7, 8, and 9, the Investigator or study staff will assess the subject for complications or adverse events, and specifically to determine if the iTotal CR or off-the-shelf total knee has been revised. It is not necessary for the subject go to the clinic for a visit, as the site can obtain the data via direct communication with them (such as via telephone or email).

The site will complete the following Case Report Form:

- FOLLOW UP
- ADVERSE EVENTS (if any)
 - REVISION FORM (if necessary)

X-rays: None

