11.7. Year 10 Follow-up Visit (\pm 4 months)

On the 10 year anniversary of the implant surgery, the Investigator or study staff will assess the subject to determine if the iTotal CR or off-the-shelf total knee has been revised.

The site will complete the following Case Report Form:

- FOLLOW UP
- KNEE SOCIETY SCORE (Surgeon portion)
- CONCOMITANT MEDICATIONS (optional)
- PAIN MEDICATIONS
- ADVERSE EVENTS (if any)
- REVISION FORM (if necessary)

The subject will be asked to complete the following function tests and questionnaires to assess long term post-operative pain and function. Note that the subject should return to the clinic to complete these questionnaires.

- THE KNEE INJURY AND OSTEOARTHRITIS OUTCOME SCORE (KOOS)
- KNEE SOCIETY SCORE (Subject portion)
- TIMED “GET UP AND GO”
- 8 METER WALK
- TIMED UP AND DOWN STAIRS

X-rays: None

11.8. **Early Termination Visit**

In the event that the study subject ends their participation in the study prior to the 10 year visit, the investigator or designated study staff will complete the following CRFs:

- SUBJECT DISPOSITION
- CONCOMITANT MEDICATIONS (optional)
- PAIN MEDICATIONS
- ADVERSE EVENTS (if any)
 - REVISION FORM (if necessary)

The Investigator or designated study staff will make every attempt to complete the following evaluations:

- THE KNEE INJURY AND OSTEOARTHRITIS OUTCOME SCORE (KOOS)
- KNEE SOCIETY SCORE (Subject and Surgeon portion)
- TIMED “GET UP AND GO”
- 8 METER WALK
- TIMED UP AND DOWN STAIRS

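### Revision, a secondary endpoint with 10 years of follow-up, is compared only by Fisher's exact test on the proportion revised, with no allowance for loss to follow-up

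*Combined protocol and SAP*

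**What the plan says.** Section 7.2 lists as a secondary endpoint "Incidence of major procedure-related and device-related complications, including revision rates", with no time point. Section 6 sets the horizon: "The study subjects will be required to complete follow-up visits at predetermined intervals for 10 years post-implantation". In years 3, 4, 6, 7, 8 and 9 (section 11.6) the site contacts the subject about complications and "specifically to determine if the iTotal CR or off-the-shelf total knee has been revised". The year 10 visit (section 11.7) also asks about revision.

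The only planned comparison is in section 15, Safety Analysis. Fisher's "Exact test will be used to compare the proportion of subjects in each study arm who have the following", and revision procedures are the third item in the list that follows. That sentence names neither an analysis time nor a population. Earlier in section 15, "The safety population will be comprised of all subjects for whom the procedure is initiated", and the AE summaries are tied to that population. No Kaplan-Meier, cumulative incidence, log-rank, Cox or person-time analysis of revision appears. The last-observation-carried-forward rule covers efficacy data only.

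The plan expects subjects to leave. Section 3 says "An additional 25% may be enrolled to account for subject discontinuation", and section 11.8 provides for a subject who stops before the 10-year visit. Section 13 has the sponsor review data periodically to determine interim revision rates.

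**The concern.** A proportion with everyone treated in the denominator ignores how long each subject was observed. A subject last seen at year 1 contributes the same as one seen unrevised at year 10. Revisions after loss are missed, so the proportion falls below the true risk.

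The comparison between arms is at stake as well as the level. Arms are filled in alternating groups of 10 without randomization, and only the functional tester is blinded (sections 3 and 10). Equal loss over a decade is therefore not guaranteed. If one arm loses more subjects, its revision proportion is pulled down further, which can create, hide or exaggerate a difference.

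Interim revision rates on crude counts would also mix subjects with short and long follow-up.

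**Working it through.** **The plan's own figures.** None exists for revision. The only power statement (section 15, greater than 80%) concerns the primary functional endpoint and does not bear on this point.

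**Inputs from the documents.** Arm size is "approximately 225-300 in the iTotal CR arm and 225-300 in the OTS arm"; 300 per arm is used below. Follow-up is 10 years. The 25% enrolment allowance offsets about 20% loss (1/1.25 = 0.80), with no time horizon attached.

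**Assumptions, not in the documents.** The safety-population denominator and all-follow-up horizon; revision risks of 4% to 10%; loss of 10% to 50% over 10 years; constant hazards; loss independent of revision; no deaths modelled; two-sided 5% level.

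**Step 1: understatement.** With true 10-year risk p and loss l, set λ = −ln(1−p)/10 and μ = −ln(1−l)/10. The expected crude proportion is λ/(λ+μ) × [1 − (1−p)(1−l)].

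- p = 6%, l = 20%: λ = 0.00619, μ = 0.02231; 0.2171 × (1 − 0.94 × 0.80) = 0.2171 × 0.248 = 5.4%.
- p = 6%, l = 30%: λ = 0.00619, μ = 0.03567; 0.1478 × (1 − 0.94 × 0.70) = 0.1478 × 0.342 = 5.1%.

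**Step 2: unequal loss, expected crude proportions (same formula).**

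- True 10% in both arms, loss 10% versus 50%: 9.5% versus 7.3%, an apparent difference where none exists.
- True 4% versus 10%, loss 20% versus 50% (heavier in the higher-revision arm): 3.6% versus 7.3%, ratio about 2.0 against a true 2.5.
- True 4% versus 10%, loss 50% versus 20% (heavier in the lower-revision arm): 2.9% versus 9.0%, ratio about 3.1.

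**Step 3: rejection rates by simulation.** 300 per arm, 4,000 to 10,000 trials per scenario and run; ranges span repeated runs.

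| True risk | Loss | Fisher | Log-rank |
|---|---|---|---|
| 10% vs 10% | 10% vs 50% | 13–14% | about 5% |
| 10% vs 10% | 15% vs 40% | about 7% | about 5% |
| 6% vs 6% | 20% vs 30% | about 3.5% | about 5% |
| 4% vs 10% | 20% vs 50% | 43–45% | 73–77% |
| 4% vs 10% | 50% vs 20% | 86–87% | 73–77% |
| 4% vs 10% | 30% vs 30% | about 71% | about 77% |

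**Step 4: source of the equal-loss gap.** In the last row, Pearson's chi-square on the same crude proportions also gives about 77%. The 6-point gap therefore comes from Fisher's conservatism, not from counting lost subjects as unrevised.

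**The case against.** The strongest reply has five parts.

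- **The horizon and denominator are inferred.** This stands. Section 15 does not say that the Fisher comparison is made at 10 years or on the safety population. The bias figures are conditional on that reading, and the silence itself needs correcting.
- **Large loss imbalances are speculative.** This stands in part. Nothing in the documents points to a 30- or 40-point gap, and the only figure corresponds to about 20% loss overall. At 20% versus 30% loss the error rate is not inflated. The understatement needs no imbalance, however, and the plan has no protection if loss does diverge.
- **Deaths.** A reader might infer that counting subjects who die unrevised also understates revision. It does not: under cumulative incidence with death as a competing event, such a subject is correctly unrevised. Only loss to follow-up causes the shortfall.
- **Power.** A reader might infer that the crude approach simply costs power. With equal loss, the gap is due to the choice of exact test. With unequal loss, rejection falls or rises depending on which arm loses more, so the problem is bias.
- **Staggered entry.** Every subject is planned for 10 years, so entry date does not shorten follow-up at the final analysis. It matters only for interim rates.

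The yearly AE summaries counted from the day of procedure do not answer the point, because no at-risk denominators are given. Nor does the fact that censoring assumes loss unrelated to revision: the crude proportion has no protection against informative loss either.

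**Conclusion.** The point holds as a defect in the analysis of one component of a secondary endpoint; the primary endpoint is untouched. On the assumed denominator and horizon, revision is understated by about 0.6 percentage points at 20% loss and 0.9 at 30%, for a true risk of 6%. The between-arm comparison is at risk only if loss differs materially. In the most unequal null case examined, Fisher's false-positive rate is about 14% against a nominal 5%. With a true difference of 4% versus 10%, its rejection rate is about 45% or 86%, depending on which arm has the heavier loss, while log-rank stays at about 73% to 77%.

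These sizes rest on assumed revision and loss rates, constant hazards and independent loss. The documents do not support saying that differential loss is expected or that the comparison is bound to mislead. They do show that follow-up time is collected for a decade and then not used.

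**What to change.** For revision, replace Fisher's test in section 15 with a time-to-event analysis:

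- Define time from implantation to first revision, censored at last contact, with death as a competing event.
- Report cumulative incidence with 95% confidence intervals by arm at 1, 2, 5 and 10 years, and use the same method for interim revision rates.
- Compare arms by an unstratified log-rank test or a cause-specific Cox model. Stratifying by up to 20 sites would leave sparse strata with few revisions.
- State the analysis time and the population.

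Fisher's test may stay for early procedure-related AEs.

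The cost is mainly plan wording, since revision forms and yearly contacts already exist. The form fields are not shown, so confirm that the revision date and last-contact date are captured (and date of death, which the competing event needs). The remaining limitation is the assumption that loss is unrelated to revision; report loss by arm and year so that readers can judge it.
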